#### 4. Study Procedures

##### Overview of Study Design

**Setting:** This research study will be conducted in Baltimore, Maryland. Maryland currently ranks 12th in the nation for incident infections with *Neisseria gonorrhoea* (GC) and *Chlamydia* (CT) among its citizens and there are disproportionate rates of infection among individuals residing in Baltimore. The Maryland Department of Health and Mental Hygiene has determined that every county is a Chlamydia hotspot and county maps demonstrate that among hotspots, the city of Baltimore is the most densely affected. Although there are extremely low rates of youth non-insurance, the utilization of primary care providers for routine health maintenance drops off considerably. The Adolescent and Young Adult Clinic at Johns Hopkins established a Title X reproductive health clinic to serve the youth of Baltimore to aid in resolving the reproductive health access issues facing urban youth. The clinic sees over 200 unduplicated positive STI cases and partner referrals annually. Patients may also be referred for treatment through the Johns Hopkins Wellness Center, the Johns Hopkins Pediatrics Emergency Department, and/or the Baltimore City Health Department clinical sites.

##### Participants and Recruitment:

Fifty dyads will be recruited from Johns Hopkins primary and affiliated institutions in the greater Baltimore metropolitan area. Index participants engaged in heterosexual relationships will be asked to recruit their main partner for enrollment in the dyadic intervention pilot. The index participant and their partner will contact study staff to be scheduled for a research visit together. Our target is to have complete data on 40 dyads so we set sample size at 50 in order to account for attrition. However, we will stop recruiting when we reach 40 participants.

**Enrollment, Consent, Randomization, and Treatment:** Recruiters will be available via phone during office and some evening hours for the Title X clinical setting. Providers for study contact will refer patients. Patients who agree to be contacted will be approached by a recruiter in person-or via phone and if eligible, the dyad will be scheduled for written informed consent and intervention procedures. At enrollment, the research staff will perform a detailed review of the EXPERIENCE

study with informed consent. While the index patient and their partner are required to present together for study enrollment, they will each be consented separately. Participants will have the option to separately consent for 1) completing both the ACASI and dyadic intervention and 2) additionally completing an in-depth interview. All study protocol study forms will be faxed to the project director at the time of enrollment and online questionnaire/ interview will be automatically uploaded to a secure server for warehousing in a central database. After enrollment, participants will be assigned to the control (1) versus intervention (2) using a computer generated randomization assignment. Envelopes based on dyadic study group number will be available to the research staff at the time of enrollment to adhere to the randomization sequence.

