### **Participants, Recruitment, Enrollment, and Consent for an In-Depth Interview Only:**

Index participants that are screened and eligible for the EXPERIENCE study intervention, but cannot recruit a partner or are not interested in the dyadic intervention will be asked to participate in a one-time in depth interview about AYA sexual health. Consent for the in depth interview only will be a separate form. We expect to enroll up to 40 participants for the in depth interview.

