### **In-depth Interviews**

For a subset of participants, we will conduct separate in-depth, semi-structured, face-to-face and/or via telephone interviews. Participants for the interview will either be 1) enrolled in the EXPERIENCE study intervention and agree to the additional and optional in depth interview or 2) agree to participate in an in depth interview only and not enrolled in the intervention. The interview will explore the social context, specifically social support; relationship qualities, modeling, and communication; and communal coping, that informs AYA partner-dyad's sexual health individually and at the partner level. For those participants that are enrolled in the intervention: the interview will occur 6-8 weeks after the dyad has completed the intervention. For those participants agreeing to an in depth interview only: the interview will be scheduled after written consent is completed. Participants will also be asked to complete a brief demographic questionnaire. We anticipate 40 individual interviews, but will continue sampling until we reach data saturation. The interviews for female and male partners will be conducted separately as to avoid any bias or influence of partner presence in given responses. An in-depth interview guide has been developed for the individual interviews. The semi-structured interview guide focuses on obtaining AYA perceptions of how social context informs sexual health. The concepts of sexual health that will be explored will include sexual experiences, partnering decisions, sexual communication, and prevention of STIs. The development of the interview guide will be an iterative process, which will allow additional questions to be added to the interview guide as necessary. Using the interview guide, the interviewer will ask open-ended questions and seek clarification or elaborations as necessary. All sessions will be audio-recorded and the interviewer will take written notes during and after each interview. During the interview, the interviewee will be asked to refer to themselves, partner(s), and/or other individuals only by an initial to protect confidentiality on recorded audio. Participants who complete the in-depth interview will receive \$50 in remuneration.

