## 7. Study Statistics

- a. Primary outcome variable. The primary outcome variable for this pilot study is feasibility of recruitment. Recruitment feasibility will be defined as the number of dyads completing the intervention out of number of eligible dyads. The feasibility of short-term retention will be calculated as the proportion of enrolled participants, who complete a follow-up interview at 6 weeks.
- b. Secondary outcome variables. The secondary outcome variable for this pilot study is acceptability, measured as participant satisfaction with their intervention experience. Participant satisfaction will be measured using a brief survey asking participants to rate their experience and qualitative feedback documented.
- c. Statistical plan including sample size justification and interim data analysis.

We will enroll a total of 50 adolescent dyads. While the choice of 50 dyads is inherently arbitrary, it is the number we feel we can realistically enroll within our limited time of this pilot study. While we won't have power to detect statistically significant differences, we will be able to examine correlations, which will be informative for future research proposals. To address each aim, we will evaluate our outcomes, feasibility and acceptability, against benchmarks from previous studies. To address aim 1, we will compare observed recruitment rates from the proposed pilot study to expected recruitment rates. Expected recruitment rates will be determined from previous studies that recruited adolescents with an STI diagnosis. Prior studies recruiting from the Adolescent Medicine Clinic have achieved recruitment rates ranging from 48 to 91%. To address aim 2, we will use a similar approach, comparing satisfaction scores to an a priori benchmark of patient satisfaction. Based on previous work, average patient satisfaction greater than 80% would be necessary to conclude that the intervention is acceptable.

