## **10. Payment and Remuneration**

Study incentives are: \$50 for the intervention visit and \$50 for the follow-up interview for each participant, both patient and partner. Those participants who elect to complete the in-depth interview will receive \$50.

Participants who agree to participate for the 2 COVID-19 calls will receive a total of \$50. After each completed call, a \$25 gift card will be sent via mail.

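### The recruitment stop at 40 participants does not say what it counts, and no reading of it agrees with the 50 dyads in Study Statistics

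*Combined protocol and SAP*

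**What the plan says.** Section 4, Participants and Recruitment, plans fifty dyads and explains the number: "Our target is to have complete data on 40 dyads so we set sample size at 50 in order to account for attrition". The next sentence reads "However, we will stop recruiting when we reach 40 participants". Section 7(c) states "We will enroll a total of 50 adolescent dyads", calls that choice arbitrary and practical, disclaims power, and mentions no earlier stop.

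The documents use the word participant in ways that bear on the unit:

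- The same recruitment paragraph says "The index participant and their partner will contact study staff to be scheduled for a research visit together". There is one index participant per dyad.
- Randomisation runs by dyad: "Envelopes based on dyadic study group number will be available to the research staff".
- Section 10 pays "for the follow-up interview for each participant, both patient and partner", so there a participant is one person.
- The interview-only section says "We expect to enroll up to 40 participants for the in depth interview", which again means individuals.

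Section 7(a) defines recruitment feasibility in dyads (those completing the intervention over those eligible) and 6-week retention in individuals (enrolled participants who complete the follow-up interview).

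**The concern.** Two consecutive sentences in Section 4 and one in Section 7 each set the size of the trial, and they do not agree. The stop sentence leaves two things open: the unit (people or dyads) and the status counted (enrolled or with complete data). Staff could close recruitment at 20 dyads, at 40, or somewhere between 40 and 50, and each could be defended from Section 4. Section 7 gives 50 outright. A later reader could not tell whether closing at 40 met the plan or departed from it.

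This is a feasibility pilot, so the number of dyads enrolled feeds directly into its main estimates: the recruitment proportion and 6-week retention.

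**Working it through.** **Inputs.** Target of 40 complete dyads, enrolled size of 50 dyads and stop at 40 participants (Section 4, Participants and Recruitment); 50 dyads with no early stop, and prior recruitment rates of 48 to 91% (Section 7). No attrition rate is stated.

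**The plan's own figure.** Implied dyad loss = 1 − 40/50 = 20%. Then 40/(1 − 0.20) = 50, which matches. Because the 20% is back-solved, this shows only that 40 and 50 fit together.

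**Three readings of the stop rule.** Expected complete dyads = enrolled dyads × (1 − loss), at 20%, with an assumed range of 10% to 30%.

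| Reading | Dyads enrolled | Share of 50 | Complete at 20% loss (10% to 30%) |
|---|---|---|---|
| 40 people | 40/2 = 20 | 40% | 16 (18 to 14) |
| 40 enrolled dyads | 40 | 80% | 32 (36 to 28) |
| Section 7, no stop | 50 | 100% | 40 (45 to 35) |
| 40 complete dyads, ceiling 50 | 40 to 50 | 80–100% | 40 if dyad retention is at least 80% |

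- *40 people.* At most 20 dyads can be complete, half the target, even with no loss.
- *40 enrolled dyads.* Forty complete would need zero loss. Treating dyads as independent at 20% loss, the chance is 0.8^40 = 0.0001, against 0.58 for at least 40 of 50. At 10% loss the figures are 0.015 and 0.99.
- *40 complete dyads, ceiling 50.* Enrolment at the stop is 40 divided by dyad retention: 40 at 100%, 45 at 90%, 48 at 85% (rounded up), 50 at 80%. This agrees with the preceding sentence in Section 4 but not with an unconditional 50.

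**Precision of retention.** Section 7 counts individuals, so n is 40, 80 or 100 people. With perfectly correlated partners, the effective n is the number of dyads. Wilson 95% intervals at an assumed 80% rate:

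| Dyads | Partners independent | Partners perfectly correlated |
|---|---|---|
| 20 | 32/40: 65.2–89.5% | 16/20: 58.4–91.9% |
| 40 | 64/80: 70.0–87.3% | 32/40: 65.2–89.5% |
| 50 | 80/100: 71.1–86.7% | 40/50: 67.0–88.8% |

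Positive within-dyad correlation puts the true interval between the two columns.

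**Precision of recruitment feasibility.** Assume that the 48–91% range applies to dyads and that every enrolled dyad completes the intervention. Eligible dyads = n/0.48 or n/0.91, rounded.

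| Dyads | At about 48% | At about 91% |
|---|---|---|
| 20 | 20/42: 33–62% | 20/22: 72–97% |
| 40 | 40/83: 38–59% | 40/44: 79–96% |
| 50 | 50/104: 39–58% | 50/55: 80–96% |

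For both estimates, 40 and 50 dyads give nearly the same interval. Twenty dyads gives a clearly wider one.

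**The case against.** The best defence is that the stop sentence follows directly on the target of 40 complete dyads and opens with a contrast. It can naturally be read as saying that 50 allows for attrition but recruitment ends once 40 complete dyads are in hand. The reference to an index participant and the dyad-numbered envelopes make a slip of unit likely. On that reading Section 4 is sound apart from one noun, and nothing is miscalculated. This stands: it would be wrong to say that every reading makes Section 4 contradict itself. But correcting the noun to dyads does not settle whether enrolled or complete dyads are meant, and either still differs from Section 7.

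A second defence is that 50 is admittedly arbitrary and no analysis requires 40 complete dyads. That limits the consequence. It does not remove the conflict, because Section 4 gives the gap between 40 and 50 a stated purpose.

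The interview figure is weak evidence for reading the rule as people. The interview-only group differs from the wider interview sample, where "We anticipate 40 individual interviews, but will continue sampling until we reach data saturation", and neither figure explains the recruitment stop. Section 10's usage is the stronger support for that reading.

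A reader might infer that the pilot will close at 20 dyads, or that the conflict undermines its statistical tests. The documents do not support either. The literal reading is available but a unit slip is at least as plausible, and no power or error rate is claimed that could be lost. Nor should the dyad-level intervals be taken as the retention precision: the protocol counts individuals, and those intervals apply only if partners' outcomes are perfectly correlated.

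**Conclusion.** Wrong as written: an internal inconsistency in the sample size, of moderate severity. The stop rule lacks a unit and a status, and none of its three readings matches the total in Section 7. Depending on the reading, enrolment is 20, 40, or 40 to 50 dyads, and expected complete dyads at 20% loss are 16, 32 or 40.

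Precision suffers materially only at 20 dyads. At 40 enrolled dyads the main loss is the complete-data target. The contradiction itself rests on the text alone. The sizes rest on the implied 20% dyad loss, an assumed 80% retention and the stated bounds on within-dyad correlation.

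**What to change.** State one stop rule in dyads, word for word the same in Section 4 (Participants and Recruitment) and Section 7(c). Say whether it counts enrolled or complete dyads, and whether 50 is a target or a ceiling. The sponsor must choose the intent:

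- **Early stop on complete data.** For example: *Recruit until 50 dyads are randomised or 40 dyads have complete data from both partners, whichever comes first; all enrolled dyads are followed and counted.* The last clause matters because follow-up takes 6–8 weeks. At an assumed 0.5 to 1 dyad per week, 0.5 × 6 = 3 to 1 × 8 = 8 dyads would still be pending at closure. With that many pending, the early stop acts only if dyad retention among those already followed is about 85% (40/47) to 95% (40/42) or better. At 20% loss the rule simply enrols 50.
- **No early stop.** Delete the sentence.
- **40 enrolled dyads.** Change 50 to 40 in both sections and restate the complete-data target as about 32, assuming 20% dyad loss.

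Cost: one sentence in Section 4 and matching text in Section 7, filed as a change in research request (Section 8c), since the COVID-19 Procedures show that enrolment was already under way. No outcome definition changes and enrolment does not exceed the stated 50. The 10 dyads between 40 and 50 carry at most 10 × 2 people × ($50 + $50) = $2,000 in visit and follow-up payments, optional interviews excluded.

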### **Participants, Recruitment, Enrollment, and Consent for an In-Depth Interview Only:**

Index participants that are screened and eligible for the EXPERIENCE study intervention, but cannot recruit a partner or are not interested in the dyadic intervention will be asked to participate in a one-time in depth interview about AYA sexual health. Consent for the in depth interview only will be a separate form. We expect to enroll up to 40 participants for the in depth interview.

### **STI Testing/Notification of Positive cases**

All participants will be offered bacterial STI Testing through the Johns Hopkins Title X program and will be notified and treated for positive results by a team clinician who will assist with arranging treatment. Three attempts will be made to reach the patient using their preferred contact number. Patients who fail to respond after three attempts via phone and/or MyChart will be sent the standard certified letter indicating that they have laboratory results that require their attention. No detailed results will be sent via mail. Documentation of attempts to reach patient will be placed in the electronic medical record to facilitate follow-up by medical providers during future visits. Patients who contact the team at any later date while the study is active will be referred for care. By law, the Johns Hopkins Hospital laboratory and the research team have an obligation to report positive cases of *Neisseria gonorrhoeae* and *Chlamydia trachomatis* to the Baltimore City Health Department (BCHD). Faxed reports will be sent to the health department.

### **Remuneration**

Index patients and partners who complete treatment and the intervention will receive \$50 remuneration for the EXPERIENCE pilot visit, \$50 for the 6-8 week telephone or in-person follow-up interview, and \$50 for participation in optional the in-depth interview. Bus tokens will be provided participants with transportation issues.

Participants who agree to participate for the 2 COVID-19 calls will receive a total of \$50. After each completed call, a \$25 gift card will be sent via mail.

*Figure 1: The EXPERIENCE Study Recruitment Algorithm*

[figure not shown]
[figure not shown]

Figure 2: Overview of Study Procedures

## Intervention

### EXPERIENCE Intervention

The EXPERIENCE intervention is designed to utilize the STI partner treatment visit to engage young males and their female partners in treatment and risk reduction interventions. Integral to the EXPERIENCE intervention is use of two effective behavioral interventions designed to reduce STI/HIV risk behaviors. We will use the Focus on the Future [FOF] for male and Sister-to-Sister [STS] for female participants. Both have 20-minute one-on-one sessions with a gender-matched health educator to guide the patient through skills-based risk reduction counseling. These interventions have been evaluated with African American males and females residing in communities with high STI rates and were found to increase condom use, reduce unprotected intercourse, and reduce new STIs among participants and are considered effective interventions for clinical implementation by the Centers for Disease Control and Prevention. The novel part of this intervention is that sexual partners will come together at the end of the individual sessions for a joint debriefing session that includes viewing of the condom negotiation videos and role-playing communication for condom use. At the end of the session with the EXPERIENCE health educators, the patient will be able to state/demonstrate: 1) understanding of the definition of STIs 2) how to prevent future STI episodes; 3) proper use of male and female condoms, 4) use of effective communication and condom negotiation strategies with their partner. Low-resource patients in our practice have been receptive to health educator support and our preliminary studies indicate that improved communication between an adolescent and her partner occurs with the support of a professional who can educate and motivate adolescents with an STI, and provide expertise on STI management. We will record a subsample (N=20) of intervention sessions for quality assurance purposes. We will use video/audio recording of dyadic intervention sessions to ensure intervention delivery is consistent with the protocol and to identify content themes to bolster our understanding of relationship dynamics and the potential of communal coping.

We will provide text message boosters related to care-seeking behavior, condom use, and condom access, over the six weeks of the study. Messages will be standardized and delivered via an automated one-way system. These messages have well tested in the field with urban adolescents and young adults. No protected health information is disclosed as a part of this communication, but youth will be encouraged to provide an extra layer of protection on existing cell phone security to allow for an additional degree of privacy related to message content. We will send a welcome message right after enrollment “welcome to the EXPERIENCE study”, followed by one text every week, including: “don’t forget to try out your new communication skills”, “Did you practice the *Experience* role play? Text the # of times you practiced together”, “Condoms prevent STDs. Stop by the clinic if you need some”, “Condoms can improve pleasure, if you need some stop by the clinic”, and “Want to up your game, practice your condom technique”. In week six, we will send “Thanks for trying EXPERIENCE, we’ll call you soon for feedback”.

We will use SMS services through TextNow for communicating with participants in both arms of the study. TextNow is one of the fastest growing technology companies in North America and has created an all IP, cloud-based mobile phone carrier and mobile messaging and application service that has more than 8 million monthly active users. It is the hybridization of Wi-Fi with cellular for texting and calling and can be enabled for use on a phone, tablet, or computer that makes this platform optimal for our pilot study. Further, TextNow has strict policies to protect the user to prevent unauthorized disclosure of information and physical, electronic, and procedural safeguards are in place according to industry standard procedures and security procedures. Research staff will be responsible for monitoring and using the online account to send standardized text-message boosters to participants in the study. Since a telephone number is created with each account, the telephone number will be recognizable to participants as EXPERIENCE communication. Finally, all participants will be encouraged to use standard safety mechanisms such as a pin or password to lock access to their cell phones by others.

### **Control Group**

Participant dyads in the control group will also receive the 20-minute Focus on the Future [FOF] for male and Sister-to-Sister [STS] for female participants one-on-one sessions with a gender-matched health educator to guide the patient through skills-based risk reduction counseling. As noted above, these interventions have been evaluated with African American males and females residing in communities with high STI rates and were found to increase condom use, reduce unprotected intercourse, and reduce new STIs among participants and are considered effective interventions for clinical implementation by the Centers for Disease Control and Prevention. **While they will check out of the intervention together and be given information to set up next steps, they will NOT engage in the facilitated dyadic group process that includes viewing the condom negotiation video, role-playing, and group debrief with the health educators.** Participants in the control arm will also receive positive health-related attention-control text messages focused on general health (healthy eating, exercise, spending time with family and friends, healthy sleep). No text messages related to relationships or condom use will be sent. As with the intervention group, we will send “Thanks for trying EXPERIENCE, we’ll call you soon for feedback” in 6 weeks. None of texts will request a response.

